Endpoints:	
Primary Endpoint: Change from baseline to 48 weeks (or last available date) in United Multiple System Atrophy Rating Score (UMSARS) total score compared with described progression rates in historical controls. We will assume that patients receiving sirolimus will have a change of 4 points less than those reported in natural history studies (see statistical section).
 
Secondary Endpoints:
 
 1. Change from baseline to 48 weeks (or last available date) in UMSARS-2 subscale score. We will assume that patients receiving sirolimus will have a change of 2 points less than those reported in historical controls. 2. Change from baseline to 48 weeks (or last available date) in UMSARS-1 subscale score. We will assume that patients receiving sirolimus will have a change of 2 points less than those reported in historical controls. 3. Magnetic resonance changes using dedicated algorithms to evaluate rate of change in diffusivity of defined areas of brain from baseline to 48 weeks. 4. Changes in retinal nerve fiber layer using optical coherence tomography from baseline to 48 weeks. 
Exploratory outcome
 
 1. Change in plasma biomarkers (exosomal alpha-synuclein particle concentration) from baseline to 48 months.

Study Population:	A total of 56 patients with multiple system atrophy will be randomized (42 to active agent and 14 to placebo)

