- CBC, CMP, CPK (8 ml of blood) and urinalysis with 24-hour urine collection
- Lipid panel (2 ml of blood)
- Sirolimus levels in blood (5 ml of blood)
- Adverse event reporting

In case the safety lab assessments are performed locally (e.g., at a local laboratory near the subjects' home), the PI or a licensed research member of the team will provide the patient with a prescription for the required tests. A research nurse, investigator or study manager will perform a phone call to assess adverse events within 7 days of the study visit.

To account for delays during the first month of treatment, Visit 7 (2-month) may be skipped to ensure that Visit 8 occurs 3 months (+/- 15 days) after the initiation of the study drug.

To maintain the blinding, the results of the sirolimus levels in blood will remain blinded to the investigators and study coordinators and delivered to the independent pharmacist in charge of determining if the sirolimus dosage should be increased or decreased.

End of study visit/early termination: the following tasks/procedures will be performed at the clinic during the termination visit (Study Visit 17):

- EKG
- MoCA
- Concomitant medications
- Physical examination
- Vitals signs
- CBC, CMP, CPK (8 ml of blood) and urinalysis with 24-hour urine collection
- Lipid panel (2 ml of blood)
- Sirolimus levels in blood (5 ml of blood)
- Retrieve study medication
- Recording of AE
- UMSARS scale
- Blood sample for exosomes (2 ml of blood)
- Retinal optical coherence tomography
- Brain MRI

We will accept a visit window of 15 days before or after the target date of this visit.

The reason for discontinuation of therapy will be documented in the source documents and captured on the CRF. In the event that the study drug is discontinued early, an early termination visit should be

completed as close to the last dose date as possible. Participants will be followed for the duration of 12 months.

If a participant is withdrawn because of an adverse event, the appropriate “Withdrawal Section” of the CRFs should be fully completed in addition to the Adverse Event module. The Independent Medical Monitor should be informed of all participants who are withdrawn for this reason. Participants will be followed for 12 months.

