- If sirolimus levels are < 5 ng/mL, the participant will be instructed to take sirolimus 2 mg two capsules daily (4 mg total dose) or matching placebo; sirolimus levels will be then measured again 7 days after the patient began taking 4 mg/day (+ 3 days). If sirolimus levels are between 5 and 20 ng/ml, the subject will continue with that dose until the next measurement of sirolimus levels on Visit (+ 3 days).
- If sirolimus levels are > 30 ng/ml with one capsule/day, the subject will be excluded from the trial due to the high risk of adverse events.

Subjects who were instructed to increase their dose to 4 mg will undergo another measurement of sirolimus levels 7 days after the previous dose adjustment (+ 3 days):

- If sirolimus levels are < 5 ng/mL, the participant will be instructed to increase sirolimus to 2 mg three capsules daily (6 mg total dose) or matching placebo. Sirolimus levels will be then measured 7 days after the patient began taking 6 mg/day (+ 3 days).
- If sirolimus levels are between 5 and 20 ng/ml, the subject will continue with that dose until the next measurement of sirolimus. If the sirolimus levels are > 20 ng/ml, the subject will be instructed to go back to the 2 mg/day dose and continue with that dose until the next measurement of sirolimus levels.

From Visit 3 to Visit 6, sirolimus level blood draw will take place 7 days (+3 days) after the previous dose adjustment has taken place (i.e., 7 days after the patient started taking the adjusted dose).

From Visit 7 onwards, subjects will be instructed to increase or decrease their sirolimus dose (between a min dose of 2 mg/day to a max dose of 6 mg/day) depending on blood levels (target: 5-20 ng/ml) and the emergence of adverse events.

Expected dose-limiting effects requiring sirolimus dose reduction are:

- Grade 2 stomatitis or mucositis
- Grade 2 lymphedema
- Grade 2 proteinuria
- Grade 2 renal failure
- Grade 3 pneumonitis
- Grade 2 diarrhea

Every attempt will be made to maintain the participant on the full dose. If the participant is unable to maintain the full dose, the minimum acceptable dose is 2 mg once a day. An attempt will be made to increase the dose with a re-challenge at a later date. Capsules should be swallowed whole with a glass of water or may be taken with food to minimize gastrointestinal side effects.

To maintain investigator and subject blinding during the clinical trial, the results of the sirolimus

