6.4 STUDY INTERVENTION COMPLIANCE

At each study visit, the investigator/site coordinator will assess the participant's compliance with the prescribed regimen for the study medication. This will include checks of protocol compliance and use of study drug in order to assess the reliability of participant-generated data. Participants who fail to comply with the study requirements may be withdrawn from the study, following consultation with the PI.

Compliance with the dosing regimen will be determined by performing study drug accountability of returned capsules and bottles of the study drug used and unused. The number of used, unused and lost capsules will be recorded on the CRF by the study coordinator.

Participants with less than 75% overall compliance during the entire study will be considered non-compliant. These participants will be included in the intention to treat analysis set and complete analysis set as defined in sections 12.3.1 and 12.3.2 respectively. However, these participants will be excluded as in the per-protocol analysis set.

Accountability records must be maintained at the site at all times. Accountability of the returned study drug should be performed and recorded at the site by the study coordinator. The participant number, the date, batch code, bottle number and quantity of study drug returned by the participant will be checked for correctness and recorded on the appropriate accountability forms.

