7 STUDY INTERVENTION DISCONTINUATION AND PARTICIPANT DISCONTINUATION/WITHDRAWAL

7.1 DISCONTINUATION OF STUDY INTERVENTION

Discontinuation from study drug does not mean discontinuation from the study, and remaining study procedures should be completed as indicated by the study protocol. If a clinically significant finding is identified (including, but not limited to changes from baseline) after enrollment, the investigator or qualified designee will determine if any change in participant management is needed. Any new clinically relevant finding will be reported as an adverse event (AE).

The data to be collected at the time of study intervention discontinuation will include the following:

- EKG
- Concomitant medications
- Physical examination
- Vitals signs
- CBC, CMP, CPK, urinalysis
- 24-hour urine collection
- Lipid panel
- Sirolimus levels in blood
- Retrieve study medication
- Recording of AE
- UMSARS scale

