7.2 PARTICIPANT DISCONTINUATION/WITHDRAWAL FROM THE STUDY

Participants are free to withdraw from participation in the study at any time upon request. An investigator may discontinue or withdraw a participant from the study for the following reasons:

- Pregnancy
- Significant study intervention non-compliance
- If any clinical adverse event (AE), laboratory abnormality, or other medical condition or situation occurs such that continued participation in the study would not be in the best interest of the participant
- Disease progression which, in the opinion of the investigator, requires discontinuation of the study intervention
- If the participant meets an exclusion criterion (either newly developed or not previously recognized) that precludes further study participation
- Participant unable to receive study drug for 15 days or more.

The reason for participant discontinuation or withdrawal from the study will be recorded on the electronic Case Report Form (CRF). Subjects who sign the informed consent form and are randomized but do not receive the study intervention may be replaced. Subjects who sign the informed consent form, and are randomized and receive the study intervention, and subsequently withdraw, or are withdrawn or discontinued from the study, will not be replaced.

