9.3 POPULATIONS FOR ANALYSES

Analyses will be performed according to the intention-to-treat principle and will include all randomized subjects who have completed, at least, 3 months of study drug.

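### The analysis set called intention-to-treat excludes anyone with under 3 months of study drug, and the synopsis last-available-date rule conflicts with week 48 plus multiple imputation in section 9.4; the likely effect is modest

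*Combined protocol and SAP*

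**What the plan says.** **Analysis set.** Section 9.3 is one sentence: analyses will be performed "according to the intention-to-treat principle and will include all randomized subjects who have completed, at least, 3 months of study drug".

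Section 6.4 deals with participants under 75% compliance: "These participants will be included in the intention to treat analysis set and complete analysis set as defined in sections 12.3.1 and 12.3.2 respectively". It adds that "these participants will be excluded as in the per-protocol analysis set". Section 9.3 defines neither a complete nor a per-protocol set, and the contents list ends at section 11, so sections 12.3.1 and 12.3.2 do not exist.

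**Follow-up after stopping drug.** Section 7.1: "Discontinuation from study drug does not mean discontinuation from the study, and remaining study procedures should be completed". Section 4.1 asks that an early termination visit be "completed as close to the last dose date as possible. Participants will be followed for the duration of 12 months". Section 7.1 includes UMSARS in the assessments made when drug is stopped. Some people may nevertheless leave altogether. Section 7.2 says "An investigator may discontinue or withdraw a participant from the study for the following reasons", and section 6.1.2 says of participants above a stated early blood level that "the subject will be excluded from the trial due to the high risk of adverse events".

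**Endpoint.** The synopsis defines the primary endpoint as "Change from baseline to 48 weeks (or last available date) in United Multiple System Atrophy Rating Score (UMSARS) total score", with the same parenthesis for UMSARS-2 and UMSARS-1. Sections 3, 8.1, 9.4.2 and 9.4.3 use week 48 without it. Sections 9.4.2 and 9.4.3 assign missing data to regression-based multiple imputation.

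**The concern.** A set defined by how long participants stayed on drug is conditioned on something that happens after randomization. Someone who stops at week 6 but returns for week 48 has the very score the primary endpoint needs, and section 9.3 leaves it out.

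The endpoint conflict concerns people who leave later. Anyone with 3 months of drug would normally have a month-3 UMSARS. Under the synopsis that score, or a later one, stands in for week 48 and almost nothing remains to impute. Under section 9.4 the week-48 value is imputed. The two rules give different data for the same person.

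The primary test compares the sirolimus arm with a fixed value, so losses in the placebo arm cannot offset either effect. What is at stake is the chance that a drug with no benefit escapes a futility finding and goes forward to phase III.

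**Working it through.** **Inputs.** Section 9.2: historical mean change 8.6, SD 9.2, threshold 8.6 − 4 = 4.6, one-sided alpha 0.05, 38 evaluable, 10% dropout, 42 enrolled on sirolimus. Schedule of activities: UMSARS after baseline at days 84, 168, 252 and 336. Assumptions, not in the documents: linear progression and a futile drug with true mean 8.6.

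**The plan's own figures.** The weighted mean is (96 × 7.5 + 50 × 10.8)/146 = 8.63, matching 8.6. The stated inputs at 80% power need 33 by the normal formula [9.2 × (1.645 + 0.842)/4]² = 32.7, or 35 by the exact t-test, against 38 stated. That gap is on the conservative side and is a separate matter. By noncentral t, the chance of declaring futility is 0.84 at n = 38 and 0.87 at n = 42; these are the reference values.

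**Last-available rule alone.** If 10% leave and contribute a fraction f of their 48-week change, the analysed mean is 8.6 − 0.10 × (1 − f) × 8.6. The fixed-SD column keeps SD at 9.2. The simulated column (200,000 trials, 4 of 42 leaving) lets early scores shrink the SD.

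| Last score of every leaver | f | Analysed mean | Fixed SD | Simulated |
|---|---|---|---|---|
| Month 3 | 84/336 = 0.25 | 7.955 | 0.75 | 0.79 |
| Month 6 | 168/336 = 0.50 | 8.170 | 0.80 | 0.82 |
| Month 9 | 252/336 = 0.75 | 8.385 | 0.84 | 0.85 |

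**3-month exclusion alone.** Dropout spread evenly puts 42 × 0.10 × 84/336 = 1.05 people before day 84. If k excluded people progress d points faster than average, the retained mean is 8.6 − k × d/(42 − k), with n = 42 − k.

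| k | d = −4 | d = 0 | d = +4 | d = +8 |
|---|---|---|---|---|
| 1 | 0.88 | 0.86 | 0.85 | 0.83 |
| 2 | 0.88 | 0.86 | 0.82 | 0.78 |
| 4 | 0.90 | 0.84 | 0.76 | 0.67 |

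The row k = 4 puts all planned dropout before month 3 and is an upper case. The range of d is illustrative.

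**Both rules, dropout spread evenly.** One of 42 is excluded; three contribute scores from months 3, 6 and 9. Then n = 41 and the mean is 8.6 − (0.75 + 0.50 + 0.25) × 8.6/41 = 8.285. The chance of declaring futility is 0.83 by simulation (0.81 with SD held at 9.2).

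**Literal decision rule.** Section 9.4.2 also says futility follows when 8.6 minus the observed change is 4 or less, that is, when the observed mean is at least 4.6. On that reading the chance is 0.98 or above in every case above.

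**Section 6.4 against 9.3.** Someone who stops before day 84 has taken drug for less than 84/336 = 25% of the planned period. If compliance is counted against planned capsules, section 6.4 keeps that person in the intention-to-treat set and section 9.3 removes them.

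**The case against.** The strongest reply is that the plan is usable as it stands. Section 9.3 fixes one set in advance, even if the label is wrong. Four sections agree on week 48, section 9.4 is the operative text, and the synopsis entry itself points to the statistical section. A reader might infer that the set and endpoint are left open to choice after the data are seen. The documents do not support that: the set is stated, and only the synopsis departs from week 48. What remains is a mislabelled set and one contradictory phrase.

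A reader might also infer a proven bias toward non-futility. An early score does understate that person's own change, but the comparison is with 8.6, and the documents do not say how dropout was handled in the historical sources. If last scores were used there too, the rule could be like-for-like. For the 3-month exclusion, nothing shows whether early leavers progress faster or slower, and nothing shows that those removed on a blood level are typical.

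Nor is section 6.4 silent on compliance: it specifies overall compliance during the entire study. Only planned versus dispensed capsules is unclear.

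Finally, month 3, 6 and 9 scores cannot be relied on to impute for people who leave the study before month 3. They may have only a baseline score and a discontinuation score. This stands, and the fix allows for it.

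**Conclusion.** The point holds as a matter of definition and consistency. The section 9.3 set is exposure-restricted and is not intention-to-treat; it can discard week-48 scores the protocol says will be collected; and the synopsis rule contradicts section 9.4. The last-available rule lowers the chance of declaring futility under linear progression; its net bias against 8.6 and the direction of the 3-month exclusion cannot be settled from the documents.

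At the planned 10% dropout, spread evenly, the chance of declaring a futile drug futile is about 0.83, close to the 0.84 planned and above the stated power of 0.80 (0.81 if early scores do not shrink the SD). The values from 0.67 to 0.79 need every leaver to go by month 3, or excluded leavers to progress several points faster, and should be read as upper cases. A reader who infers from them that the trial's decision is seriously compromised goes further than the documents allow. The correction is still worth making before analysis because it is specific and cheap.

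**What to change.** 1. Make the primary set all participants randomized to sirolimus who took at least one dose and have a baseline UMSARS. Use any week-48 UMSARS collected after drug was stopped. Label the set modified, since it is not full intention-to-treat either. Keep the 3-month set as a labelled sensitivity analysis.
2. Delete the last-available-date parenthesis from the three synopsis UMSARS endpoints, so that week 48 with the planned multiple imputation governs. Impute from baseline and whatever later UMSARS exists, including the discontinuation assessment in section 7.1. Add a delta-adjusted sensitivity analysis that reports where the decision changes.
3. Reconcile section 6.4 with section 9.3: state whether compliance is counted against planned or dispensed capsules, define or delete the complete and per-protocol sets, and correct the references to sections 12.3.1 and 12.3.2.

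**Cost.** Wording changes, about 1 to 4 more records in the primary set, and the sensitivity analyses above. There is a statistical price. If the drug just meets 4.6 on treatment and k early leavers revert to 8.6, the mean over all 42 is 4.6 + 4k/42. That gives 4.695, 4.790 and 4.981 for k = 1, 2 and 4, and the false-futility chance rises from 0.05 to 0.057, 0.065 and 0.084. The 3-month sensitivity set would show this. Dropping the last-available rule also gives up some conservatism: with a true mean of exactly 4.6 and 10% dropout, that rule holds false futility at 0.03 to 0.04 rather than 0.05.

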9.4 STATISTICAL ANALYSES

9.4.1 GENERAL APPROACH

The two treatment groups (sirolimus and placebo) will be compared for baseline characteristics. This analysis will include demographic data and MSA history. The continuous variables will be examined using the two-sample t-test or Wilcoxon rank sum test when appropriate. For testing the assumption of normality prior to applying parametric approaches (i.e., two sample t-test), visual inspection of the normality plots as well as the Kolmogorov Smirnov test of normality will be used. We will use 5% level of significance for the test of normality. If the underlying data were to be non-normal, we will use non-parametric approaches for analyzing the data (i.e., Wilcoxon rank sum test). Categorical variables will be examined for differences between groups using the Chi-Square test or the Fisher's exact test when appropriate.

9.4.2 ANALYSIS OF THE PRIMARY EFFICACY ENDPOINT

The primary outcome endpoint (UMSARS total score) will be analyzed by comparing the mean decline in total UMSARS score in the active sirolimus group (UMSARS total score at week 48 minus UMSARS total score at baseline) with the pre-specified fixed value of 8.6 (SD: 9.2) using a one-sample t-test. If the difference between the fixed value of 8.6 minus the UMSARS total score in the active sirolimus group is 4 or less, the null hypothesis will be rejected, indicating futility.

Missing data will be addressed by using a regression-based multiple imputation model (78)

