4 STUDY DESIGN

4.1 OVERALL DESIGN

To determine whether to test sirolimus in a large phase 3 trial, we propose to conduct a clinical trial of sirolimus in MSA using a futility design. A futility design under the null hypothesis assumes that sirolimus will slow the progression of the disease, whereas the alternative hypothesis assumes no benefit of sirolimus. If the null hypothesis is rejected (i.e., futility of sirolimus to slow progression of MSA), major phase 3 studies will be discouraged, whereas non-futility will offer strong support for a phase III trial to detect clinical efficacy.

To test this hypothesis we will perform a single-center, randomized, double blind, placebo-controlled, phase-II, futility trial, chosen as an efficient approach to determine if sirolimus would be worthy of future investigation in larger, more definite trials. This trial was designed to compare the mean value for the primary outcome measure, change in total Unified Multiple System Atrophy Rating Scale (UMSARS) score from baseline to week 48, between the sirolimus arm and a pre-specified fixed value, representing a 4-point reducing in the expected mean decline without treatment; this fixed value was obtained using data from previously completed a large natural history study(39) and the placebo arm of a recently completed clinical trial in MSA (40). The 4-point reduction was based on the recently reported minimally clinically important decline (MICD) in the total UMSARS score of 3.5-points (38).

The null hypothesis is that sirolimus will reduce the mean decline in the total UMSARS score over 12 month by, at least 4-points, compared with the expected (fixed) value obtained from the historical controls. If the null hypothesis is rejected, then the drug would be considered futile for further investigation in MSA. If the null hypothesis is not rejected, sirolimus would be considered for a phase 3 clinical trial.

Thus, the primary goal is to evaluate the effect of sirolimus on progression of MSA, including autonomic, cerebellar and parkinsonian features as measured by the UMSARS, a relevant clinical measure of disease progression. Secondary goals are to determine if there is any effect on neuroimaging (brain MRI) and ophthalmological (retinal OCT) biomarkers of the disease. As exploratory aim we will determine if there are any changes in plasma α Syn exosomes, as surrogate markers of autophagy.

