9.2 SAMPLE SIZE DETERMINATION

This study is a randomized, double blind placebo-controlled futility trial in which the primary outcome measure value (UMSARS total score) in a cohort of patients with MSA taking active agent will be compared to a known value from historical controls previously published in the literature. The primary outcome measure was used to calculate the sample size.

The primary statistical analysis will involve a comparison of the mean absolute difference in the active sirolimus group with a pre-specified fixed value, constituting a 4-point reduction in the expected mean increase in the UMSARS total score over 48 weeks without treatment. The expected mean increase in total UMSARS outcomes were obtained from the *U.S. Natural History Study of MSA* (n=96) (39), that reported that the total UMSARS score at 12 months increased a mean of 7.5 (SD: 8.4) absolute points from baseline. Also data from a phase III double-blind placebo-controlled 12-month clinical trial with rifampicin in MSA performed in the U.S. (40) (which was found to be ineffective to slow the progression of the disease) showed that in patients taking placebo (n=50) the total UMSARS score at 12 months increased a mean of 10.8 (SD: 10.7) absolute points from baseline. A weighted analysis of these two populations showed the pooled total UMSARS score at 12-months in patients with MSA in large studies performed in the U.S. had increased a mean of 8.6 (SD: 9.2) points from baseline.

Also, recent studies (38) have determined that the minimally clinically important difference (MCID) in the total UMSARS score is 3.5 points after 48-weeks from baseline.

Taking into consideration this MCID, for this trial, we will assume a promising difference in the UMSARS total score of 4 points between those taking active agent and the historical controls. Specifically, our null hypothesis is that patients receiving sirolimus will have a UMSARS total score progression of only 4.6 points at week 48 higher than baseline, compared to a progression of 8.6 points at week 48 from baseline reported in historical controls from natural history studies and placebo-controlled trials of MSA. Our alternate hypothesis is that sirolimus will be futile to slow the progression of the disease in patients with MSA. The statistical definitions are as follows:

$H_0: \theta_E - \theta_p \leq 4$ where $\theta_p = 8.6$ points increase at week 48 from baseline described in historical controls

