$H_0: \theta_E \leq 4.6$ points increase at week 48 from baseline

$H_1: \theta_E > 4.6$ points increase at week 48 from baseline

Therefore, assuming an alpha of 0.05, and a power of 0.8 (one sided, as patients with MSA have not been reported to improve spontaneously) to detect a progression of 4.6 points (i.e., 8.6 minus 4) in the UMSARS total score after 48-weeks from baseline we will need to enroll 38 patients in the active agent arm. Anticipating a 10% for dropouts rate, we will need to enroll 42 patients in the active agent arm.

This trial will include a placebo group to facilitate blinding in a 3:1 proportion. However, statistical comparisons for the primary and secondary efficacy outcome measures will be performed between the active agent arm and the historical controls. We will therefore enroll 14 patients in the placebo arm.

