9.4.3 ANALYSIS OF THE SECONDARY ENDPOINT

In order to maintain the overall type I error at the 0.05 level, an hierarchy will be employed as follows: If the primary endpoint is found to be significant at a significance level of 0.05, then the first key secondary endpoint will be tested; if this endpoint is found to be significant in a significance level of 0.05, then the second key secondary endpoint will be tested and so on. The key secondary endpoints and their order in the hierarchy are:

UMSARS sub-scores: The secondary outcome endpoint (UMSARS-1 and UMSARS-2 scores) will be analyzed by comparing the mean decline in total UMSARS-1 and UMSARS-2 score in the active sirolimus group (UMSARS-1 and UMSARS-2 at week 48 minus UMSARS-1 and UMSARS-2 at baseline) with the pre-specified fixed value of 4.5 (SD: 5.5) in each score using a one-sample t-test.

Brain magnetic resonance imaging: The secondary outcome endpoint (putaminal diffusivity) will be analyzed by comparing the mean increase in Trace(D) score in the active sirolimus group (Trace(D) score at week 48 minus Trace(D) score at baseline) with the pre-specified fixed value of 0.07 ($\times 10^{-3}$ mm²/sec) using a one-sample t-test.

Retinal optical coherence tomography: The secondary outcome endpoint (retinal nerve fiber layer

thickness) will be analyzed by comparing the mean decline in RNFL thickness in the active sirolimus group (RNFL at baseline minus RNFL at week 48) with the pre-specified fixed value of 3.7 μm using a one-sample t-test.

Concentration of exosomal αSyn particles: This exploratory outcome endpoint will be analyzed by comparing the mean change in αSyn exosomal particles concentration (week 48 minus baseline) in the active sirolimus group with the placebo group.

In all cases missing data will be addressed by using a regression-based multiple imputation model (78)

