9.4.5 PLANNED INTERIM ANALYSES

Interim efficacy analysis will be performed when 24 patients have completed the trial.

If the efficacy pre-specified criteria are fulfilled, the trial will be stopped for overwhelming efficacy. These pre-specified criteria are:

- The average increase in the total UMSARS score is 4 points or less from baseline to week 48 in patients taking active agent – OR –

- The average increase in the total UMSARS score from baseline to week 48 in patients taking active agent is significantly lower than in patients taking placebo with a $P < 0.001$.

If the futility pre-specified criteria are fulfilled the trial will be stopped for futility. These pre-specified criteria are:

- The average increase in the total UMSARS score is at least 7 points or more from baseline to week 48 in patients taking active agent - OR –
- The average increase in the total UMSARS score from baseline to week 48 in patients taking active agent is significantly higher than in patients taking placebo with a $P < 0.001$.

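### Section 9.4.2 as written declares futility at any observed benefit of 4 points or less, so the final test calls a drug with exactly the target benefit futile 50% of the time, against a stated one-sided alpha of 0.05

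*Combined protocol and SAP*

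**What the plan says.** Sections 9.1 and 9.2 set a futility design. The null hypothesis is a mean 48-week increase in UMSARS total score of 4.6 or less on sirolimus, that is, a benefit of at least 4 points against the historical 8.6. The alternative is an increase above 4.6. Section 4.1 says that rejecting the null makes the drug futile for further investigation. The sample size is justified by "assuming an alpha of 0.05, and a power of 0.8 (one sided").

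Section 9.4.2 gives the primary analysis in two steps. It compares the mean change in the sirolimus group "with the pre-specified fixed value of 8.6 (SD: 9.2) using a one-sample t-test". It then states the decision: "If the difference between the fixed value of 8.6 minus the UMSARS total score in the active sirolimus group is 4 or less", the null is rejected and futility is concluded.

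Three other places bear on this:

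- Section 9.2 describes the comparator as "a pre-specified fixed value, constituting a 4-point reduction in the expected mean increase in the UMSARS total score over 48 weeks without treatment", and Section 4.1 as "a pre-specified fixed value, representing a 4-point reducing in the expected mean decline without treatment". On both descriptions the fixed value already contains the 4-point reduction, so it is 4.6.
- Section 9.4.3 opens the secondary hierarchy with "If the primary endpoint is found to be significant at a significance level of 0.05".
- Section 9.4.5 adds an interim look with its own cut-offs on the active-arm mean. The trial stops for efficacy if "The average increase in the total UMSARS score is 4 points or less" and for futility if "The average increase in the total UMSARS score is at least 7 points or more".

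**The concern.** The condition in Section 9.4.2 is a cut-off on a point estimate, placed exactly on the null boundary. A test that controls the error at 5% needs the observed mean to exceed 4.6 by a margin for sampling variation, and the sentence allows none. It contradicts the alpha in Section 9.2 and the significance level in Section 9.4.3.

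A separate inconsistency, which does not produce the 50%, is the reference value. A t-test against 8.6 asks whether progression on sirolimus differs from historical progression. It does not test the null at 4.6. Section 9.4.2 also does not say how the t-test result enters the decision.

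This rule decides every trial that reaches the final analysis. False futility is the costly error in this design, because the protocol says rejection will discourage a phase III study. An observed mean between 4.6 and about 7.1 is futile under Section 9.4.2 and not futile under the 5% test that Section 9.2 implies, so the conclusion could depend on which reading is chosen after the data are seen.

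**Working it through.** **Inputs.** Section 9.2: historical mean 8.6, SD 9.2, target benefit 4 (null boundary 8.6 − 4 = 4.6), one-sided alpha 0.05, power 0.80, 38 evaluable and 42 enrolled on sirolimus. Section 9.4.5: interim when 24 patients have completed, with mean cut-offs of 4 and 7.

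**The plan's own figures.** The pooled mean reproduces: (96 × 7.5 + 50 × 10.8)/146 = 8.63. So does the n-weighted SD: (96 × 8.4 + 50 × 10.7)/146 = 9.19. The 38 does not reproduce. The normal approximation gives (9.2 × (1.645 + 0.842)/4)² = 32.7, so 33, and the noncentral t gives 35. The plan is therefore somewhat larger than its inputs need; at n = 38 the 5% t-test has 83.8% power. This does not affect the main point, because the 50% below depends on neither n nor SD.

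**Literal rule at the final test.** The condition 8.6 − mean ≤ 4 is equivalent to mean ≥ 4.6. With SE = 9.2/√38 = 1.492, P(futility) = 1 − Φ((4.6 − true mean)/1.492).

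| True benefit | True mean change | P(declared futile), as written |
|---|---|---|
| 4 | 4.6 | 0.500 |
| 5 | 3.6 | 0.251 |
| 6 | 2.6 | 0.090 |
| 0 | 8.6 | 0.996 |

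The error falls to 5% only at a true benefit of 4 + 1.645 × 1.492 = 6.5 points.

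**A 5% test against 4.6.** The critical mean is 4.6 + t(0.95, 37) × 1.492 = 4.6 + 1.687 × 1.492 = 7.12. The observed benefit must then be 8.6 − 7.12 = 1.48 or less, not 4. Power at a true change of 8.6 is 0.838. If all 42 enrolled patients enter the analysis, the critical mean is 6.99 and power is 0.870. Both thresholds take the observed SD as 9.2.

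**Joining the two steps of Section 9.4.2.** Requiring both one-sided significance below 8.6 and an observed benefit of 4 or less gives, by simulation at a true mean of 4.6, futility in about 34% of trials at n = 38 and 37% at n = 42. This reading does not restore 5% either.

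**With the interim stops.** The interim futility cut-off alone has these error rates at a true mean of 4.6:

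- 18 active patients: SE = 9.2/√18 = 2.168, and P(mean ≥ 7) = 1 − Φ(2.4/2.168) = 0.134.
- 24 active patients: SE = 9.2/√24 = 1.878, and P(mean ≥ 7) = 1 − Φ(2.4/1.878) = 0.101.

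The overall rates below come from simulating 400,000 trials with normal data, SD 9.2 and final n = 38. Both mean cut-offs are binding and the P < 0.001 comparisons with placebo are ignored.

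| Active patients at interim | True mean | Overall futility, as written | Overall futility, final test corrected |
|---|---|---|---|
| 18 | 4.6 | 0.431 | 0.152 |
| 24 | 4.6 | 0.452 | 0.117 |
| 18 | 8.6 | 0.981 | 0.894 |

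If only the futility stop binds (18 active, true mean 4.6), the figures are 0.512 and 0.152.

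**The case against.** The strongest reply is that a correct rule can be assembled from the documents. The hypotheses at 4.6 are in Sections 9.1 and 9.2, the one-sided 0.05 in 9.2, the one-sample t-test in 9.4.2, and the reference to significance at 0.05 in 9.4.3. The disputed sentence follows directly after the t-test is named, so it could be read as restating the alternative region, with the t-test supplying the criterion. On that reading the 50% never arises and the defect is loose drafting plus a wrong reference value.

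A 5% test probably was intended. But no section states that rule. Section 9.4.2 is where the final decision is defined, and its only explicit criterion is the point-estimate cut-off. The test it names uses 8.6, so following the section exactly cannot give a 5% test of the null. A correction is needed on either reading.

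Two further objections concern scope. The 50% is not the trial-level error if the interim stops bind; that is true, and the trial-level figures are 43% to 45%. The interim cut-offs are also a distinct defect resting on further assumptions. They matter here because correcting Section 9.4.2 alone does not bring overall false futility to 5%.

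The first H0 line in Sections 9.1 and 9.2 (θ_E − θ_p ≤ 4) reads as θ_E ≤ 12.6. A minus sign may have been lost in text conversion, and the next line gives the operative 4.6. This is minor and needs only a check against the source file.

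**Conclusion.** The concern holds. Read literally, the final decision rule has a 50% chance of declaring a drug with exactly the target benefit futile, ten times the stated alpha. That figure needs only a symmetric sampling distribution of the mean. The 25% and 9% at benefits of 5 and 6 points assume SD 9.2 and n = 38.

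At trial level, with both interim mean cut-offs binding and the P < 0.001 rules ignored, false futility at a true change of 4.6 is about 43% if 18 of the 24 interim completers are on sirolimus (an assumption from the 3:1 allocation) and about 45% if all 24 are. Correcting the final test alone leaves about 15% and 12%. Because this is the primary decision rule and it contradicts the design's stated error rate, it must be fixed before the analysis.

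**What to change.** In Section 9.4.2, keep the definition of the endpoint (week 48 minus baseline) and the missing-data sentence. Replace the comparison with 8.6 and the 4-or-less rule with:

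> The null hypothesis θ_E ≤ 4.6 is tested with a one-sided, one-sample t-test of the mean change in the sirolimus group against 4.6 at alpha 0.05. Futility is declared only if p < 0.05.

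Write the first H0 line in Sections 9.1 and 9.2 as θ_p − θ_E ≥ 4.

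Reconcile Section 9.4.5 with the 5% level in one of two ways: set the interim futility cut-off and the final critical value jointly so that overall false futility at 4.6 is 5%, or keep the cut-offs and state the overall error rate that results.

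Section 9.4.3 should be checked for the same mismatch. Its MRI and OCT t-tests use 0.07 and 3.7 as references, while the null boundaries in Section 9.1 are 0.03 and 1.45.

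The cost is a wording amendment and one operating-characteristics calculation. At the final test, the chance of declaring a drug with no benefit futile falls from 99.6% to about 84%, still above the planned 80%. With the present interim stops and 18 active patients it falls from about 98% to about 89%. The Section 9.4.2 correction needs no additional patients. The power cost of recalibrating the interim to an overall 5% has not been worked out here.
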